4 OBJECTIVES

The goal of this Phase I application is to prove the feasibility and small scale pilot efficacy of WC Services to increase CRC screening. We propose the following specific aims:

Specific Aim 1: Test the feasibility of WC Services to achieve CRC screening for non-adherent Medicaid clients. **Milestone 1a:** Achieve colonoscopy by a minimum of 60 out of 200 ($\geq 30\%$) patients contacted. **Milestone 1b:** Achieve CRC stool screening for 70 of the 140 colonoscopy non-adherent clients. **Milestone 1c:** WC Services will be revised to produce a new prototype to test in a Phase II based on findings.

Specific Aim 2: Develop an algorithm for predicting CRC screening outcomes following intervention services. **Milestone 2a.** Develop models based on existing R01 data to predict intent and CRC screening behaviors. **Milestone 2b.** Revise this R01 model incorporating new measures collected prospectively with 80% of clients contacted (n=160) to identify variations for likelihood of stool test v. colonoscopy completion.

Research Questions: **a)** Will Medicaid clientele, health insurers and physicians find WC Services usable and valuable for CRC screening? **b)** Will clients accept services and obtain colonoscopy or stool tests? **c)** Will current and/or new measures show predictive potential within Medicaid clientele for colonoscopy and/or stool tests? **d)** Will WC Services be able to increase screening enough to demonstrate potential for improving quality metrics for health insurance companies and primary care practices? Answering these research questions and achieving these aims (**Milestone 3:** Phase I Report), position us for a larger randomized controlled evaluation in Phase II while addressing important CRC screening disparities for the community and health care system.

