Proposed Data Collection (Milestone 2b). For this secondary data analysis, as a part of the Aim 1 methods described above, navigators will invite all clients contacted to complete assessment items via telephone. Based on prior research and navigation experience, we know that clients are willing to complete health assessments and surveys of up to ~130 questions by phone if incentivized. This telephone assessment includes 118 self-report questions all of which have been used by the current team members with African American and Medicaid clients. However, we have never combined all of these items, and expect this to increase our capacity to identify impactful predictors. Based on prior experience, we are adding a Patient Activation Measure (PAM),²⁹⁻³² Process of Change (POC)^{33,34} for CRC screening and a 3-item unpublished, Navigator Subjective Assessment/Predictor (NSAP) by the navigator at the completion of the other questions (based on recent experiences by [name] and [name]). A similar data analysis strategy will be applied here. The 118 items will be used to predict differentiation of screeners from non-screeners as well as, among screeners, those who chose FIT versus colonoscopy (COL). Together, these are expected to significantly increase our predictive capacity for colonoscopy outcomes. We anticipate (Milestone 2b) being able to complete the survey with at least 160 clients during this Phase I.

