Expected outcomes of Aim 1 will prove whether or not *WC Services* can achieve $\geq 65\%$ CRC screening of clients reached. **Milestone 1a:** Achieve colonoscopy by a minimum of 60 out of 200 ($\geq 30\%$) patients contacted. **Milestone 1b:** Achieve CRC stool screening for 70 of the 140 colonoscopy non-adherent clients (50% of clients refusing/ineligible for colonoscopy). Beyond these milestones, additional **feasibility benchmarks** include: a) Acceptance/satisfaction by clients per client satisfaction phone surveys; b) Acceptance/satisfaction by YourCare and MCCC per self-report and any screening metrics improvement; c) Navigation services, number of screening tests per week/month, hours spent for cost analysis; d) Acceptance/satisfaction by GI physicians and facilities per self-report, number and quality of bowel preps and no-shows; e) Process evaluation of all. **Milestone 1c:** *WC Services* will be revised based on outcomes and benchmark measures from Aim 1, to produce a new prototype to test in a larger randomized study in Phase II.

AIM 2: Proposed Data Analysis (Milestone 2b). Update the Screening Engagement Model: Utilizing standard Bayesian methods, the data collected in Aim 1 from the (expected) $n=160$ intent-to-screen clients will be used to: A) update the coefficients of the Screening Engagement Model; and B) determine whether PAM, POC and NSAP measures should be incorporated. The performance of the updated model will be assessed using the AUC, sensitivity, and specificity (with 95% confidence intervals as appropriate). If the AUC of the resulting model is 0.8 (or 0.9), indicating reasonable performance, then the corresponding 95% confidence interval width would be 0.14 (or 0.10). *FIT versus COL:* Within the sub-set of subjects that were screened, measures will be compared between those who chose FIT versus COL using the Mann-Whitney U test. In Aim 1 we expect 60 COL and 70 FIT subjects, which provides 80% power (at $\alpha=0.05$) to detect a 0.5 standard deviation difference. Additionally, a multi-variable logistic regression model may be considered to identify potential independent factors associated with screening choice.

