Expected Outcomes. **Milestone 2a:** Develop models based on R01 data to predict intent and CRC screening behaviors. **Milestone 2b:** Revise this R01 model incorporating new measures collected prospectively with 80% of clients contacted ($n=160$) to identify variations for likelihood of FIT v. COL completion. From these analyses we will produce a new prototype of a Screening Engagement Model to test in a larger trial for a Phase II study. **Milestone 3:** Phase I Report will be prepared to include all Milestones and feasibility benchmarks.

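### Milestone 2b sets no performance criterion for the prediction model, so the Screening Engagement Model prototype goes to Phase II whatever its accuracy, judged on an AUC not corrected for optimism

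*Combined protocol and SAP*

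**What the plan says.** Milestone 2b appears in the Synopsis, in Section 4 and under Expected Outcomes in Section 8. Section 8 words it as "Revise this R01 model incorporating new measures collected prospectively with 80% of clients contacted" (n=160), for the purpose of distinguishing likely FIT completion from likely colonoscopy completion. Section 5, under Proposed Data Collection, ties the milestone to a survey count: "We anticipate (Milestone 2b) being able to complete the survey with at least 160 clients during this Phase I".

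On performance, the Aim 2 analysis in Section 8 says: "The performance of the updated model will be assessed using the AUC, sensitivity, and specificity", with 95% confidence intervals. An AUC benchmark appears once, in "If the AUC of the resulting model is 0.8 (or 0.9), indicating reasonable performance", where it introduces expected interval widths of 0.14 and 0.10. Section 5 adds that, if there are several models, they will be ranked on these measures.

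Expected Outcomes then says: "From these analyses we will produce a new prototype of a Screening Engagement Model to test in a larger trial". No condition is attached. Research question (c) in Section 4 asks: "Will current and/or new measures show predictive potential within Medicaid clientele for colonoscopy and/or stool tests".

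**The concern.** Aim 2 hypothesises that a set of measures will predict effectively which clients take up screening, and the Synopsis expects the completed aims to yield assessment tools for a randomised Phase II trial. A milestone for that aim should be able to separate a model that predicts from one that does not. Milestones 1a and 1b can do this for Aim 1, because they are outcome targets (60 of 200 colonoscopies, 70 of 140 stool tests) that can be missed.

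Milestone 2b has no such target. A revised model with an AUC near 0.5 completes it as well as one with an AUC of 0.9. The one performance figure a reader would use to judge the model comes from the data used to update it, with up to 118 candidate items. A weak model may therefore not look weak. What is at stake is an uninformative go-forward for the algorithm and no agreed basis for answering question (c) at the level of the model.

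**Working it through.** **1. The plan's own figures reproduce.** Inputs from Section 8: n=160, AUC 0.8 or 0.9. The class split is not given; 80/80 is assumed. Hanley-McNeil:

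SE² = [A(1−A) + (n1−1)(Q1−A²) + (n0−1)(Q2−A²)] / (n1·n0), with Q1 = A/(2−A) and Q2 = 2A²/(1+A).

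- A=0.8: Q1=0.6667, Q2=0.7111. SE² = (0.16 + 79×0.0267 + 79×0.0711)/6400, so SE = 0.0351. Width = 2×1.96×0.0351 = 0.138 (plan: 0.14).
- A=0.9: SE = 0.0253, width 0.099 (plan: 0.10).
- With 104 screened and 56 not (65% of 160, taken from the Aim 1 target), the widths are 0.134 and 0.093.

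The precision statement is therefore sound for a score fixed in advance.

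**2. What Milestone 2b depends on.** If 160 is read as a pass mark, the chance of meeting it is P(X ≥ 160) with X ~ Binomial(200, p), where p is the true survey completion rate:

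| p | P(at least 160 of 200) |
|---|---|
| 0.75 | 5.8% |
| 0.80 | 54.2% |
| 0.85 | 97.8% |

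The AUC does not enter this calculation.

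**3. Could n=160 support a criterion?** At the 104/56 split with a fixed score:

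- AUC 0.5: SE = 0.048, 95% interval 0.5 ± 1.96×0.048, about 0.41 to 0.59.
- AUC 0.8: SE = 0.0342, lower limit 0.8 − 1.96×0.0342 = 0.733.
- A lower limit above 0.5 needs an observed AUC of about 0.59; a lower limit above 0.7 needs about 0.77.

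For a fixed score, the planned size separates chance from the plan's own standard of reasonable performance.

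**4. Optimism in the apparent AUC.** Null simulation: 118 independent noise items, 160 clients, 104 screened, 1,000 runs, best k items chosen and scored on the same data.

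| k | Mean apparent AUC (truth 0.5) |
|---|---|
| 1 | 0.63 |
| 3 | 0.70 |
| 5 | 0.74 |

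This uses simple selection, not the plan's bootstrap and Bayesian procedure, so it is illustrative.

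**5. How often would a criterion be met?** Rule: lower 95% limit of the AUC above 0.5, at 104/56. The left column is a score fixed in advance (simulated, DeLong SE). The right column selects the top 5 of 118 independent items inside 10-fold cross-validation, uses a Hanley-McNeil limit, and ignores the R01 prior.

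| True or best attainable AUC | Fixed score | Selected and cross-validated |
|---|---|---|
| 0.50 | 2.8% | about 13% |
| 0.65 | 90% | about 28% |
| 0.70 | 99% | about 49% |
| 0.80 | about 100% | about 95% |

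The right column varies with how many items carry signal: runs with 5 or 10 true signals gave 13–14%, 24–27%, 35–49% and 85–97%. Its null rate of 13%, against a nominal 2.5%, shows that an interval formula for a fixed score is too narrow once selection has been done on the data.

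**The case against.** The strongest reply is that this is a Phase I feasibility study. A prototype here is a deliverable to be tested, and Milestone 1c also produces one without a threshold. Milestone 3 reports everything, so an AUC near chance with its interval would be visible. Bootstrap selection and the R01 prior should both reduce overfitting. All of this is fair and limits the seriousness. It does not supply a rule, and less overfitting is not the same as a corrected AUC. Ranking models is relative: the best of several poor models still ranks first.

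Three stronger readings are tempting and should not be made.

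- **That the step to Phase II depends on the survey count.** The sentence in Expected Outcomes carries no condition at all. Elsewhere 160 is described as expected or anticipated, so the binomial figures in step 2 describe a pass mark the plan may not intend.
- **That no result could count against the measures.** Section 8 uses the data to decide whether PAM, POC and NSAP enter the model and compares measures between FIT and colonoscopy choosers at α=0.05. Section 5 selects predictors at a strict exit level. Individual measures can fail. Only a rule for the model as a whole is missing.
- **That a simple rule would reject a chance-level model about 97% of the time and almost never reject a useful one.** That holds only for the fixed-score column in step 5, not for a model selected and updated on the same 160 clients.

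Nor would a chance-level tool be put into use: the plan says it goes to further testing.

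**Conclusion.** The point holds as a missing decision rule combined with an uncorrected performance estimate. No section sets a minimum AUC, sensitivity, specificity or confidence limit for meeting Milestone 2b or for carrying the model forward. The reported AUC could mislead: under no signal it averages 0.70 to 0.74 when 3 or 5 of 118 noise items are selected and scored on the same clients.

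The size of that optimism rests on independent items, simple selection and no prior. The 104/56 split is also an assumption: the 65% target refers to clients reached, while Section 8 describes the 160 as clients intending to be screened. The textual finding needs none of these assumptions.

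The gap should be closed before the Aim 2 analysis. It does not affect Aim 1, the sample size or participants' safety.

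**What to change.** 1. **Section 8, Aim 2 analysis.** Report the AUC of the updated model corrected for fitting on the same data, with variable selection and updating repeated inside each bootstrap sample or cross-validation fold, and with an interval that reflects this. Also report the AUC of the unmodified R01 model on the new clients. That score is fixed in advance, so the stated interval widths apply to it more directly.
2. **Milestone 2b (Synopsis, Section 4, Section 8) and the Expected Outcomes sentence.** Carry the prototype to Phase II as a predictive tool only if a pre-stated minimum is met. One example is a lower 95% limit of the corrected AUC above 0.5, with the plan's 0.8 as the target for reasonable performance. Otherwise the Phase I report states that predictive potential was not shown. The sponsor should justify the value; 0.5 is a low floor.
3. **FIT versus colonoscopy.** State a matching criterion for discrimination among screened clients, since that is the milestone's stated purpose and a model of screened versus not screened could pass without addressing it. If 80% of the expected 60 colonoscopy and 70 FIT clients complete the survey, this rests on 48 and 56 clients.

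Cost: no new clients or data, but more than a change of wording, because the validation method and its interval must be specified. The milestone can then be missed. Under the simplified cross-validation in step 5, the example rule would be met about 28% of the time at a best attainable AUC of 0.65 and about 95% at 0.80. The plan's actual procedure, with its R01 prior, should be simulated before a value is fixed.

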9 INFORMED CONSENT

Human Subjects Involvement and Characteristics. Witness CARES, LLC will develop and obtain business agreements with YourCare and Mercy Comprehensive Care Center (MCCC) as required by these businesses to allow them to provide lists of their clients who are ages 50 and over and are non-adherent to CRC screening over the past year (i.e., no stool testing in past 11

months or colonoscopy for over 9 years). The clients will be Medicaid or Medicaid/Medicare subscribers. Uninsured patients may be included from MCCC, but will only be eligible for services to obtain FIT tests through the NYS Cancer Services Program.

Once Witness CARES, LLC receives these lists they will do the following:

- 1) Begin calling clients and explaining that they are working collaboratively with their insurer or clinic to provide additional services for clients needing CRC screening. This initial call will allow WC Services to determine working/accurate telephone numbers and confirm that clients have not obtained CRC screening. We anticipate calling clients from the list (expected to be up to 2000 clients) until we successfully reach at least 200 clients. Witness CARES, LLC will send insurer and health clinic the lists with results of non-working numbers, patients no longer at numbers, etc.
- 2) Use an existing CRC navigation assessment to inquire about the client's knowledge and understanding of CRC screening. Depending on the results of this assessment, the navigator may a) determine some basic information about potential services the client will need to obtain screening (stool or colonoscopy), and establish a plan with the client to provide these services with a timeline; or b) send the client additional information by mail, email or text for a smart phone for the client to review, and establish a call-back appointment time.
- 3) For clients planning to be screened, the navigators will begin the process of working through the services needed by the client (for either completion of the stool test) or the colonoscopy to include some or all of the following: a) delivery of a FIT or Cologuard test (dependent on Medicare coverage); b) telephone followup and assurances that stool test is completed, mailed and results are received; c) assistance to obtain the Rx for colonoscopy; d) determination of acceptable GI physician and screening location for colonoscopy; e) appointment for colonoscopy is made; f) education for and assistance with the prep materials and telephone followup for assurance that the materials are purchased (or we deliver them), the client understands the procedure; questions are answered; g) transportation plans are secured if needed, including escort or family member to accompany client; h) telephone followup the day before scheduled colonoscopy to assure prep is/will be completed; i) assistance as needed to transport the client for the colonoscopy appointment; j) telephone followup to assess client satisfaction with the procedure and understanding of results.
- 4) For clients reluctant to be screened, or who do not complete stool tests or colonoscopy appointments, navigators will conduct additional follow-up and motivational interviewing to encourage completion. After 3 attempts, the navigator will obtain permission from the client to mail them additional information and how to contact the navigator for future assistance, and then the client will be removed from the active list for navigation.
- 5) All clients reached will be invited to complete a ~130-item survey (based on measures from our R01 CRC study plus two new measures – see Table 1) to obtain answers to questions that will be analyzed to study how to more accurately predict CRC screening compliance. Clients will be offered a \$20 gift card as an incentive for completing this survey by the navigator over the phone.
- 6) Following successful CRC screening (fecal test or colonoscopy), clients will be contacted by telephone to assess qualitative measures of satisfaction with the navigational services as well as the screening services received. These findings will be used to refine and revise the WC Services.

Sources of Materials. During the telephone calls, and specifically the survey assessment, survey data will include responses to questions on CRC knowledge, fear of colonoscopy, questions about CRC screening referrals (e.g. regular relationship with PCP physicians, having

had discussion or referral for CRC screening, personal experience or knowledge of individuals in the health care system), Process of Change, Patient Activation Measure and demographic (e.g. age, gender, education level, insurance status) and prior CRC screening (see Table 1). Educational materials will include printed brochures and evidence-based videos about CRC screening.

Table 1. Study Measures			
R01 Measure for Milestones 2a & 2b	Source	Reliability	Use in Previous Studies
Benefits/Barriers (Both FIT and Colonoscopy)	Rawl et al 2001	$\alpha > 0.65$ Rawl et al 2001	Janz et al 2007 & 2003; Madlensky et al 2004; Menon et al 2003
Affective Associations with screening (including Fear of Colonoscopy)	Crites et al 1994; items selected based on pilot study above	$\alpha > 0.88$ [name] et al 2009; Pilot study described above	[name] et al 2007 & 2009; Simons et al 1998
Cognitive/Affective Risk Perceptions	Weinstein et al 1995 ; Zajac et al 2006	Single item measures	Moser et al 2007; Waters et al 2011; [name] 2010 & 2009
Cancer Worry	Lerman et al 1991		Lerman 1991
Screening Behavior/Intentions	Vernon et al 2004	Test-retest > 90% Vernon et al 2008 Concordance > 0.80 Partin et al 2008	Emmons et al 2009; Janz et al 2007; Nelson et al 2004
Demographics (e.g.,SES, Insurance, PCP, PCP visits, screening referrals)	[name] et al 2011; [name] et al 2010	Single item measure	[name] et al 2011; [name] et al 2010
Prospective New Measures for Milestone 2b only			
Patient Activation Measure®	Hibbard et al. 2005	Reliability coefficients (with ethnic minorities) = $\geq .70$	Alexander, Heard and Mittler 2014; Serper et al. 2014; Greene, Hibbard 2012
Process of Change for CRC Screening	Manne et al. 2002	CFI=0.785	Duhamel et al 2011

Potential Risks. There are no physical risks posed by this study. The types of questions asked in the surveys and the types of information presented in the interventions are not different from those that might be asked or presented by a health care provider and thus do not pose greater than minimal risk. Although the chances of psychological distress are minimal, any psychological distress will be monitored by the staff and if appropriate, participants will be offered a referral to Psychology/Psychiatry Staff, if warranted. Potential benefits include increased knowledge about colorectal cancer and screening as well as information about how to get screened and/or assistance and services to successfully complete screening. Although we cannot guarantee that participants may benefit directly from study participation, especially those completing the survey alone, but those clients obtaining colonoscopy may prevent CRC cancer or find it earlier. Study participants in our prior studies have reported they enjoyed providing researchers with greater knowledge of their experience in hopes of facilitating cancer prevention and in possibly benefiting others. Given the potential gains to participants the ratio of risk to benefits is quite low and reasonable.

2. ADEQUACY OF PROTECTION AGAINST RISKS

Recruitment and Informed Consent. Witness CARES, LLC staff members will work with our customer clients (YourCare and MCCC) to obtain and recruit clients from their "gaps in care" lists. Information sheets and oral consent over the phone will be used for the telephone survey. The Business Agreements will provide coverage for offering the navigational services.

The key elements of the informed consent procedure which will be explained to the participants are: 1) the research status of the study; 2) the prospect of psychological risk and the provisions for it; 3) the lack of guarantee of benefit from participation, 4) the confidentiality of subjects responses to all study measures; 5) the voluntary nature of the study; 6) the lack of consequences to medical care of the decision to consent or to refuse to participate; 7) the receipt of the gift card for participating, and 8) the freedom to withdraw from the study or to refuse to answer specific questions at any time.

Before the survey is conducted, staff member will explain: 1) the nature and purpose of the research endeavor, 2) that participation in the research component is completely voluntary, and 3) that data collected from participants will be confidential and assessed, evaluated and reported as aggregate data, as well as precautions taken in the storage of the data. The study staff member will verify that the women and men who wish to participate meet the study's eligibility criteria as described above. The staff member will solicit and respond to any and all inquiries.

For the colonoscopy procedures, individual, hospital/facility/physician specific consents will be signed and this is beyond the scope or responsibility of Witness CARES, LLC or the study staff.

Protection Against Risk. Oral consent will be received from participants prior to their completion of study questions for the telephone survey. These include questions on CRC knowledge, fear of colonoscopy, cancer worry, perceived risk, questions about regular relationship with physicians and having had discussion or referral for CRC screening), affective and cognitive associations with CRC and questions about demographics (e.g. age, gender, education level, insurance status) and prior CRC screening. The data will be recorded on the phone and on a pen and paper survey form (to be developed into an electronic record). The survey data will be identified with a coded ID in order to add CRC screening outcomes to the record for analysis. Reporting of the data is completely anonymous and de-identified.

Participants may refuse to participate without penalty. Participant records and responses are identified by an assigned identification code of the client and the client list will be kept locked and separated from the interview data.

